5.1.7. Rationale for Amendment (b)

The protocol is amended for the following reasons:

As part of the continuous monitoring of safety, PK, and laboratory markers in patients with HCC, the sponsor noted that patients are staying on study beyond 4 months. Furthermore, the 300 mg/day dose appears to have no evidence of increased toxicity. There appears to be no difference in the number of patients at the 160-mg/day and the 300-mg/day dose who stayed beyond 4 months. In addition, in all other ongoing trials with LY2157299, the dose of 300 mg/day was selected for future clinical development.

Preliminary PK data from the first interim analysis (n=20 patients) suggest that patients administered 300 mg/day have higher exposures than previously observed for the same dose level (Study JBAH) during the treatment period. LY2157299 appears to be fully eliminated after the 14-days off period of a cycle (additional PK sampling is added to study the clearance of LY2157299). The lowest exposure level (ie, most conservative) in the most sensitive nonclinical species administered LY2157299 in a clinically relevant dosing schedule (2 weeks on/2 weeks off) in which cardiac effects were observed was 24 $\mu\text{g}\cdot\text{hr}/\text{mL}$ (Table JBAK.2). The findings at this dose level (150 mg/kg) consisted of a single male rat (n=10/group) with minimal inflammation in the aortic valve and ascending aorta. Administration of 300 mg/day to patients with HCC may result in higher than anticipated exposures; however, due to the clinical safety profile observed thus far and the benefit:risk in this patient population, this approach is considered acceptable.

Because of these reasons and the lack of substantial evidence that the 160-mg/day dose is superior to the 300-mg/day dose, the dose of 300 mg/day is selected for the continuation of this trial.

For Part B, it was decided to evaluate the effects of LY2157299 in patients with AFP <1.5x upper limit of normal (ULN) to have an overall assessment of LY2157299 efficacy in all HCC patients. At the time of the decision to focus on the 300-mg/day dose, 74 patients were randomized.

The study design will be modified as follows:

- Part A: Evaluation of LY2157299 in Child-Pugh A or B7 patients with AFP $\geq 1.5x$ ULN. After stopping the 160-mg/day dose arm, all newly enrolled patients will be treated at the 300-mg/day dose.
- Part B: Evaluation of LY2157299 in Child-Pugh A or B7 patients with AFP <1.5x ULN

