9.4. Method of Assignment to Treatment

In Part A, patients who meet all criteria for enrollment will be randomized to receive 1 of 2 doses of LY2157299 after completing the screening at Visit 0. Assignment to dose cohorts will be determined by a computer-generated random sequence using an interactive voice response system (IVRS). The randomization method used should result in approximately equal numbers of patients in each dose cohort (no more than a difference of 4 patients between the 2 dose cohorts at any planned analysis while enrollment into both cohorts occurs). To achieve between-cohort comparability for stratification factors, the randomization should ensure as much balance as possible between AFP levels (≤ 400 ng/mL and >400 ng/mL), etiology (alcohol, viral hepatitis, other), and whether sorafenib naive or not, both at interim (after 20 and 80 patients have been randomized) and final analyses, the order of priority being as listed. It is important to implement a system such that treatment of eligible patients is not delayed.

The decision to stop enrolling into Cohort 1 was made based on the results from the additional data review. The remaining patients that were to be assigned to Cohort 1 (until 70 patients have been treated) who have elevated AFP levels and who meet all criteria for enrollment will be assigned by the IVRS to receive the LY2157299 300-mg/day dose (ie, transferred to Cohort 2) after completing the screening at Visit 0.

In Part B, patients who have a AFP level <1.5 x ULN and who meet all criteria for enrollment will be assigned by the IVRS to receive the LY2157299 300-mg/day dose after completing the screening at Visit 0.

Enrollment into Part B will continue during the interim analysis of Part B.

In Part C, patients who have not received prior systemic treatment and who meet all criteria for enrollment will be assigned by the IVRS to receive either the LY2157299 80 mg BID or the LY2157299 150-mg BID dose after completing the screening at Visit 0.

In Part D, patients who meet all criteria for enrollment will be assigned by the IVRS to receive either the LY2157299 80-mg BID or the LY2157299 150-mg BID dosage after completing the screening visit.

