With Amendment (c), the study planned to enroll approximately 190 patients: 109 patients have been enrolled in Part A (37 in Cohort 1, 72 in Cohort 2); 40 are planned for Part B, and 40 for Part C (amended to enroll Child Pugh A patients who had not received any prior systemic therapy and were to be treated with LY2157299 plus sorafenib in a safety lead-in followed by an expansion at the selected dose).

With Amendment (d) and the addition of Part D, an additional 15 patients may be enrolled. With Amendment (e) and the addition of Part E, approximately 23 additional patients may be enrolled.

The primary objective of the study now is to characterize the TTP distributions, the effect on TGF- β -associated serum biomarkers (for example, TGF- β , AFP, E-cadherin) and the relationship between biomarker response and efficacy endpoints of:

- 1) Each of the 2 doses of LY2157299 in second-line patients or patients ineligible to receive sorafenib with HCC who have elevated AFP levels (Part A, Cohorts 1 and 2),
- 2) In second-line patients or patients ineligible to receive sorafenib with HCC who have AFP levels $<1.5x$ ULN dosed at 300 mg/day (Part B),
- 3) In first-line patients with HCC treated with 2 doses of LY2157299 in combination with sorafenib. If the decision in Part C is to use only 1 treatment group in the expansion cohort, the results from patients at the other dose will simply be listed.
- 4) In second-line patients with HCC treated with LY2157299 given for 21 days on followed by 7 days off (Part E).

For efficacy endpoints, no formal hypothesis testing based on a priori power calculations is planned; rather differences in various endpoints (eg, hazard ratios for TTP, OS) between appropriate treatment groups will be estimated. Since Part C patients are different in 2 ways from patients in Parts A and B (first-line versus second-line and treated with LY2157299 in combination with sorafenib compared to LY2157299 monotherapy, respectively), the only estimate of differences between Parts A and/or B with Part C will be between Part C and the sorafenib-naive patients from Parts A and B. The interpretation of any estimate will be considered in light of the size of this subgroup.

Data from patients from Part D and E will be summarized separately from the data in Parts A, B, and C.

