12.2.8. Clinical Efficacy Analyses

Kaplan-Meier analysis will be performed on the observed distribution of TTP (Kaplan and Meier 1958) for each dose in Part A, Part B, Part C, Part D and Part E, with parameter estimates of the TTP median and quartiles being reported. All parameter estimates will be quoted together with their 90% confidence limits. The hazard ratio between the observed TTP distributions of each cohort in Part A will be estimated, recognizing that since 1 dose cohort did not enroll to its full

complement, the precision of the HR will be lower than originally planned. The hazard ratios between the 300 mg/day cohort in Part A and Part B cohort will also be estimated. In addition, the hazard ratio between a subgroup of sorafenib-naïve patients in Parts A and B and patients in Part C may be estimated. The interpretation of any estimate will be considered in light of the size of this subgroup.

Alternative distributions of TTP times, such as exponential Weibull (estimating a shape parameter may also be considered) where median TTP and its 90% CIs will be reported. Individual parameters, such as TTP rate after specific time points (for example, after 12 months on treatment) will be estimated from the TTP distribution.

Secondary efficacy measures include other time-to-event parameters, and these will follow the same analyses as described above.

The overall response rate (ORR) for each cohort in Part A, Part B, Part C, Part D and Part E will be estimated by dividing the total number of confirmed responders by the number of patients who received at least 1 dose of study treatment. The clinical benefit rate will be estimated for each treatment group by dividing the total number of patients experiencing benefit by the number of patients who received at least 1 dose of study treatment. A patient is considered to have received benefit if they achieve a confirmed response, CR or PR, or SD per RECIST v1.1 or mRECIST. Both mean and exact confidence limits will be provided for each group (Cohort 1 and Cohort 2 in Part A, Part B, Part C, Part D and Part E, as well as estimates of differences between 2 cohorts in Part A, between Parts A and B at 300 mg/day, and between sorafenib-naïve patients in Part A and Part B with those in Part C. The interpretation of any estimate in the latter comparison will be considered in light of the size of this subgroup.

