5.2. Analysis Sets

Efficacy and safety analyses will be based on all enrolled patients receiving at least one dose of LY2157299.

Pharmacokinetic (PK) analysis will be conducted on patients who received at least one dose of study drug and have had samples collected.

Pharmacodynamic (PD) analysis will be conducted on patients who have received at least one dose of the study drug and have had samples collected.

Pharmacogenomic analysis will be conducted on patients from whom a valid assay result has been obtained from whole blood and serum, and tumor tissue blocks from diagnostic or surgical tumor samples.

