5.3.8. Efficacy Analyses

5.3.8.1. Clinical Efficacy Analyses

Time to tumor progression (TTP) is the primary clinical endpoint for this study. A listing of TTP, including date of first dose, date of progression, date of death, censoring and TTP duration will be listed. The time to progression distribution will be characterized using the Kaplan-Meier method. Kaplan-Meier curves of TTP will be presented. Median TTP, quartiles and TTP rate after specific time points (for example, after 12 months and 24 months on treatment) will be estimated from the survival curves. All these parameter estimates will be reported together with their 90% confidence intervals. A comparison between the observed TTP distributions of each dose cohort will be performed using the log rank test and the p-value reported. The hazard ratio between the observed TTP distributions of different cohorts/parts (or different subgroups of interest) will be estimated. The interpretation of any estimate will be considered in light of the size of this subgroup. The list of possible comparisons are:

- 1) In part A: 160 vs 300 mg (160 reference)
- 2) Between Part A and Part B 300 mg groups (Part A reference)
- 3) Between Part A, Part B and Part C (sorafenib naïve or not)

Sensitivity analyses using alternative distributions of survival times, such as Weibull (with and without estimating a shape parameter) will be explored and median TTP with its 90% CIs will be reported.

Secondary time-to-event parameters will follow the same analyses described above.

Additional exploratory analyses on clinical endpoints such as TTP or OS will be carried out. Prognostic factors, such as baseline AFP levels, etiology, and whether sorafenib naïve or not, may be added to the time-to-event models to explain the variability in duration of progression. Analyses using subgroup identification methods, such as classification and regression tree (CART) (classification and regression tool) may also be carried out.

The best overall response rate and clinical benefit rate together with their 90% exact confidence intervals will be reported for each dose cohort in Part A, Part B and Part C. These rates will be compared between dose cohorts using Chi-squared tests. Odds ratios, 90% confidence intervals and p-values will be reported. Cohorts comparison should follow the above list for types of comparisons for TTP and OS.

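### The Part A 160 vs 300 mg comparison pools about 35 non-randomised patients into the 72 at 300 mg with no randomised-only estimate, and SAP 5.3.3 groups overall survival by a post-baseline event

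*SAP*

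**What the plan says.** **Dose comparison.** SAP 5.3.8.1 lists "In part A: 160 vs 300 mg (160 reference" as the first of its planned cohort comparisons. For TTP it says: "A comparison between the observed TTP distributions of each dose cohort will be performed using the log rank test and the p-value reported". A hazard ratio is also estimated. Secondary time-to-event endpoints follow the same analyses, and response rates are compared by chi-squared test with odds ratios and p-values. SAP 5.2 sets the population: "Efficacy and safety analyses will be based on all enrolled patients receiving at least one dose of LY2157299".

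**How patients reached 300 mg.** Protocol 5.1.7 states: "At the time of the decision to focus on the 300-mg/day dose, 74 patients were randomized". Protocol 12.1 says Cohort 1 stopped at 37 patients and gives the final sizes: "109 patients have been enrolled in Part A (37 in Cohort 1, 72 in Cohort 2". After closure, protocol 9.4 says the remaining eligible patients with elevated AFP "will be assigned by the IVRS to receive the LY2157299 300-mg/day dose (ie, transferred to Cohort 2". The synopsis confirms that randomisation ended with Amendment (b).

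**Existing safeguards.** SAP 5.3.6.1 compares baseline characteristics of 300 mg patients enrolled before and after 160 mg was dropped, because of a concern that the later ones might have a worse prognosis. In SAP 5.3.8.1, prognostic factors "may be added to the time-to-event models to explain the variability in duration of progression", and the synopsis makes the stratification factors similarly optional. Protocol 12.2.8 warns only that "the precision of the HR will be lower than originally planned".

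**OS.** From Amendment (b), asymptomatic patients could stay on treatment after objective progression. SAP 5.3.3 responds by considering OS separately for two groups: those who discontinued for objective progression before the amendment, and those who discontinued for progression or symptomatic deterioration after it. Protocol 12.2.1 asks only that the amendment under which each patient enrolled be captured.

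**The concern.** This is the trial's only randomised contrast, and recommending doses is a secondary objective. A reader who sees a hazard ratio and log-rank p-value for the two Part A doses will take them as randomised evidence, when about half of one arm was added afterwards. Any change over time in case mix, sites or care is then mixed with the dose effect. If later patients did worse, the pooled estimate counts against 300 mg; if they did better, it flatters it. The sponsor saw the prognosis risk but committed to no analysis that removes it.

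The OS grouping has a different defect: membership depends on when and why a patient stopped treatment, which is unknown at baseline. A patient enrolled early reaches the later group only by staying on treatment until the amendment, so that group is enriched for slower disease. Patients who stopped for other reasons, or have not stopped, belong to neither group. No stratum, subset or covariate is defined.

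**Working it through.** **1. The plan's own figure.** Protocol 12.1 gives about 80% power for a hazard ratio of 1.5 at two-sided 20%, with around 129 events among 140 patients. I take exponential TTP with medians of 3 and 4.5 months (ratio 1.5), uniform accrual A = 24 months, follow-up F = 6 months and λ = ln 2/median:

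P(event) = 1 − [exp(−λF) − exp(−λ(A+F))]/(Aλ)

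This gives 0.955 and 0.895, so 70 × 0.955 + 70 × 0.895 ≈ 129.5 events, which reproduces the 129. Power = Φ(√129 × ln 1.5/2 − 1.282) = 84.6%, so the stated 80% is conservative. Nothing below depends on it.

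**2. Non-randomised patients.**
- Randomised to 300 mg: 74 − 37 = 37.
- Assigned later: 72 − 37 = 35, and 35/72 = 49%.
- If 37 is not exact, the balance limit of 4 in protocol 9.4 allows 33 to 41 randomised to 300 mg, hence 31 to 39 later.
- Protocol 12.2.14 says 64 had been treated at the decision; SAP 5.3.2 says 74. Taking 64 as the randomised total gives 64 − 37 = 27 at 300 mg, a gap of 10 that is out of line with the limit of 4. Protocol 12.1 describes 64 as patients dosed and in the database at the data review, which fits better.

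**3. Effect of pooling.** Cox simulation with 37 + 37 + 35 patients, no dose effect, exponential TTP with median 11.9 weeks (protocol 5.1.5.2), about 10% censoring and 20,000 trials per value. Drift is the assumed hazard of the later 35 relative to the rest.

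| Drift | Pooled HR (300 vs 160) | 90% CI coverage | Log-rank rejection at 0.10 | RMSE of log HR |
|---|---|---|---|---|
| 0.8 | 0.89 | 85% | – | 0.251 |
| 1.2 | 1.09 | 87% | 13% | 0.236 |
| 1.3 | 1.12 | 85% | 15% | 0.248 |
| 1.5 | 1.19 | 79% | 21% | 0.280 |

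(– : not recorded.) The 37 vs 37 estimate stays at HR 1.00 with about 90% coverage, 10–11% rejection and RMSE 0.255–0.259. The RMSEs cross at drift of about 1.35. With 31 or 39 later patients, the pooled HR at drift 1.2/1.3/1.5 is 1.08/1.11/1.17 or 1.10/1.14/1.22.

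**4. Precision.** SE = 1/√(D·a(1−a)), where D is events and a the 160 mg share. At the design event rate of 92.5% (assumed to carry over):
- 37 vs 72: D = 100.8, a = 0.339, SE = 0.21.
- 37 vs 37: D = 68.5, a = 0.5, SE = 0.24.

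The simulation gives 0.217 and 0.251; 0.251/0.217 = 1.16.

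**5. OS grouping with no true difference.** 108 scenarios of 200,000 patients, early:late 74:35, scans every 6 weeks, post-progression survival tuned to the reported median OS of 31.4 weeks. Assumed:
- early accrual over 52, 65 or 78 weeks before the amendment;
- later enrolment starting 0 or 13 weeks before it and ending 22 weeks after;
- weekly discontinuation for other reasons 0–0.012, and death without progression 0–0.006;
- mean 0 or 6 weeks on drug after progression under the new policy.

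Median OS is 27–34 weeks in the *before* group and 35–48 in the *after* group. The ratio is 1.2–1.4 if treatment stops at progression and 1.3–1.6 if it continues a mean of 6 weeks. Between 14% and 43% of patients fall in neither group. Grouped by enrolment period, both medians are about 31. Further single-scenario runs gave 26 vs 34–39 and 29 vs 37 weeks, in the same direction.

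**The case against.** - **The comparison is descriptive.** Protocol 12.1 dropped formal comparisons, SAP 5.3.3 plans estimation only, and protocol 5.1.7 shows 300 mg was selected for other stated reasons before these analyses. This stands and limits the consequence to a misread estimate. The SAP still attaches p-values to the contrast.
- **It is partly handled.** The baseline comparison is a real commitment, the optional covariates include the randomisation factors, and SAP 5.3.8.1 would allow hazard ratios in subgroups of interest. All true, but none commits to the randomised estimate, and a baseline table does not correct a hazard ratio.
- **The drift is assumed.** It is. On the same simulation, pooling has the smaller overall error at mild drift. That is a good reason to keep the pooled analysis and show both.
- **The 35 is inferred, and the 64/74 mismatch may be explained.** The count is derived, not stated. The Amendment (e) change summary appears to show the protocol's treated count revised from 74 to 64, with the older SAP keeping 74. Confirming the count remains sensible.
- **SAP 5.3.3 does not define a before-versus-after contrast.** Correct, and the simulated medians depend on invented rates. But the only rule written there is post-baseline, and the protocol already points to a better variable.
- **A later SAP may exist.** The one supplied is the third version, aligned to Amendment (c) and approved in October 2013, while protocol 12.2.8 foresees further versions before Parts D and E. The conclusion applies to the text supplied.

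**Conclusion.** The concern holds on both counts and should be fixed, with medium confidence about its practical size. About 49% of the 300 mg arm was not randomised, an inference that rests on reading 74 as the number randomised when 160 mg closed. How far this moves the hazard ratio is unknown, because it depends on a drift the documents do not quantify: assumed hazards from 0.8 to 1.5 in later patients move a true 1.0 to between 0.89 and 1.19. The direction of the OS grouping error follows from the definition of the groups; its size depends on the assumed accrual and discontinuation patterns. The two problems also compound: the added 300 mg patients come largely from the period when treatment beyond progression was allowed, so dose and policy are confounded for OS. Because the analysis is descriptive and the dose was already selected, the risk is misinterpretation rather than a false formal claim.

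**What to change.** 1. In SAP 5.3.8.1, add the 160 vs 300 mg comparison of TTP, OS and response in patients randomised while both cohorts were open (about 37 vs 37). Confirm the count from the IVRS and reconcile protocol 12.2.14 with SAP 5.3.2. Present this as the randomised estimate beside the 37 vs 72 comparison, and state that the latter includes non-randomised patients.
2. In SAP 5.3.3, replace the discontinuation-based OS grouping with grouping by the amendment in force at first dose, as protocol 12.2.1 implies. Note that earlier enrollees who progressed after Amendment (b) were also under the new policy, so this grouping does not isolate the policy change.
3. Label both as post hoc. The further SAP version foreseen in protocol 12.2.8, or the clinical study report, can carry them.

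The cost is two text changes and one re-run on a subset. The randomised estimate has an interval about 16% wider on the log scale. At the design event rate its power for a hazard ratio of 1.5 at two-sided 20% is about 65%, against 74% for the pooled comparison. The pooled analysis is kept, so nothing is lost there.

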5.3.8.2. Pharmacodynamic Analyses

Pharmacodynamic (PD) markers (for example, AFP, AFP L3, PIVKII, E-cadherin, TGF- β 1 (possibly adjusted for PF4 level)) will be analyzed using a mixed-effects model with patient as a random effect and dose, sampling time, and baseline values as fixed effects. Depending on the data, an appropriate variance-covariance structure will be added to the model. Serum concentrations will be log transformed prior to analysis.

Comparisons between subgroups in baseline AFP (AFP: $\leq 400\text{ng/mL}$ or $>400\text{ng/mL}$ [the threshold value of 200 ng/mL will also be used]), etiology (viral hepatitis, alcohol, other), and use of sorafenib may be carried out by either including these terms as fixed effects in the above models or as separate analyses. Interactions terms will be included if appropriate. The decision to perform this analysis will be made based on whether there is any evidence that the variability of data between the different subgroups and the actual number of patients enrolled in each subgroup.

Geometric means by dose and time together with 95% confidence intervals will be provided for this analysis. Ratio of means and 95% confidence intervals between doses for each subgroup of interest and between subgroups of interest within each dose will be estimated from the models.

Plot of means over time will be provided for each biomarker in the dosing cohorts. Bar plots with ratio of means and 95% confidence intervals may be provided for the subgroup analyses.

In addition, each marker will be summarized descriptively by subgroup of interest, dose and time.

Percent of maximum change from baseline in AFP level will also be summarized: $>0\%$, 0-25% reduction, 25-50% reduction, $>50\%$ reduction. Waterfall plots of maximum reduction and line plots of raw data and percent change from baseline over time will also be provided.

Previously reported AFP response criteria will be evaluated.

The association between changes in PD markers and clinical endpoints will be explored to determine their value as predictive biomarkers of drug effect on clinical outcome. Biomarkers with categorical data will be listed with baseline values, first post dose value in the hypothesized direction of change and time to this post baseline value. Biomarkers with continuous data will be listed with baseline values, first maximum change from baseline based on their hypothesized direction of change and time to this first maximum change. The patient's TTP will also be included in the listing to relate biomarker responses to therapy with improved TTP. A descriptive summary of patients with specific level of maximum change from baseline and time to this maximum change may be provided.

For biomarkers with categorical data, frequency and percentages will be used to summarize the data.

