5.1.3. Pharmacodynamic Efficacy Endpoints

Elevated AFP is a marker of disease progression in HCC patients. Hence, a treatment effect can be measured by following the kinetics of AFP reduction during the treatment period and a sustained reduction of 50% over 3 months is a relevant change suggesting a treatment effect.

Other AFP response criteria will be studied including the following definition : AFP response is >20% decrease in AFP from baseline (samples collected closest to first dose) during 8 weeks of treatment.

Elevated TGF- β 1 (possibly adjusted for PF4 level), though less validated, correlated with poor clinical outcome in HCC patients. Hence, a reduction in TGF- β 1 levels is another marker of activity of a beneficial treatment effect.

The protein, E-cadherin, is associated with EMT and elevated levels of this marker is found in aggressively growing HCC. Hence, a change in kinetics of its level may reflect treatment effect.

Additional PD endpoints (for example, Fibrotest, T-cells counts, AFP L3, PIVKII) may be considered for analysis.

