Analysis of the mean fold change from baseline of biomarker concentrations levels will be estimated from a mixed-effects model with sampling time, dose and their interaction as fixed effects, baseline levels (either as a continuous variable or categorical) as a covariate and patient as a random effect. The choice of variance-covariance structure will depend on the data. Biomarker concentrations will be log transformed prior to analysis. Specific details of these analyses will be provided in the TFL shells and requirements.

If at the second interim analysis, when a total of 40 patients had been enrolled at each dose and followed as described, results of the comparison between the doses were still inconclusive, the decision to either continue enrollment into both doses or to choose 1 dose was to be made after discussions between the investigator, Lilly, and study statistician.

However, the planned second interim analysis described in Amendment (a) was not carried out. The decision to carry out an additional data review is described in Protocol section 5.1.5.1. Based on this review, the decision was to close Cohort 1 and continue enrollment until 70 patients have been enrolled in Cohort 2. At the time of the decision, 74 patients had been treated.

As part of Amendment (b), the second interim analysis for Part A is now planned after the 70th patient has enrolled into Cohort 2 and started Cycle 1. The purpose of this analysis is to help inform the decision to prepare for further development of the compound in patients with HCC

with elevated AFP levels. This analysis was completed in December 2012 (Faivre et al. 2013). Safety, efficacy (TTP, ORR, clinical benefit rate) and PK will be assessed at the second interim analysis. Pharmacodynamic markers and health outcome data will also be reviewed at this second interim to gain preliminary insight to patient benefit in this indication for inclusion into the end of Phase 2 briefing document.

The purpose of the interim analyses in Part B and Part C is to prepare for further development of the compound and to inform the decision as to whether all second-line HCC patients, irrespective of baseline AFP levels, and all first-line Child-Pugh A or B7 patients may benefit from treatment with LY2157299. Safety, efficacy and PK will be assessed at these interim analyses.

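### SAP 5.3.8.2 sets an unwindowed maximum marker change beside TTP; longer TTP usually means more samples, so an uninformative marker without adverse drift tends to look favourable (low priority)

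*SAP*

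**What the plan says.** SAP 5.3.8.2 says that associations between marker changes and clinical endpoints "will be explored to determine their value as predictive biomarkers of drug effect on clinical outcome". For continuous markers the listing gives the baseline value and the "first maximum change from baseline based on their hypothesized direction of change and time to this first maximum change". For categorical markers it gives the "first post dose value in the hypothesized direction of change and time to this post baseline value". Neither rule has a time window. The SAP adds that the patient's "TTP will also be included in the listing to relate biomarker responses to therapy with improved TTP". An optional summary follows: "A descriptive summary of patients with specific level of maximum change from baseline and time to this maximum change may be provided". Earlier in the section, "Percent of maximum change from baseline in AFP level will also be summarized" in bands, also without a window.

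The section gives no landmark, time-dependent covariate or adjustment for the number of samples. SAP 5.3.10 carries the Part A and B analyses over to Part C.

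Protocol Attachment 1 sets the sampling in Parts A to C:
- AFP, AFP L3, E-cadherin, PIVKA II and TGF-beta: Days 1 and 14 of each cycle, and Visit 801.
- MAP panel and Fibrotest: Day 14 only; Fibrotest has no Visit 801 sample.
- Immunophenotype: Day 1 of each cycle, and Visit 801.
- After one year on study, tests are needed on Day 1 only.
- None of these markers is scheduled in follow-up after Visit 801.

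**The concern.** TTP runs from first dose to objective progression, and progression is a reason to stop study drug (protocol 8.3.1). A patient who progresses late has therefore usually been sampled more often than one who progresses early. The maximum of a series grows with its length even when the marker only fluctuates around a constant. Someone who reads down the listing would see larger responses beside longer TTP, and could credit the marker with a relationship produced by the sampling. This is the familiar problem of comparing responders with non-responders when response needs time to be observed. At stake is which markers are judged promising, since the listing exists to inform that judgement.

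**Working it through.** No figure in the plan quantifies this, so there is nothing to reproduce. The check asks how strong an association the listing shows when the truth is none.

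**Inputs from the documents.** Within-patient CV 44% for AFP (protocol 12.2.14, SAP 5.3.2). Scans every 6 weeks from Cycle 2 Day 14. Sampling as above. 47 patients in Part C (protocol 7.1). Median TTP 11.9 weeks in Part A and 18.0 weeks in Part B (protocol 5.1.5.2); 18.3 weeks in sorafenib-naive monotherapy patients (protocol 5.1.8), used as a stand-in for Part C.

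**Assumptions.** Independent log-normal noise, exponential TTP, no deaths before progression, stopping hazard 0 or 2% per week, treatment past progression 0 or 4 weeks, AFP drift 0 or 2% per week.

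**Step 1, noise.** Log-scale SD = sqrt(ln(1 + 0.44²)) = 0.42. A change from baseline has SD 0.42 × √2 = 0.595. With one sample, the chance of an apparent reduction of at least 50% is Φ(ln 0.5 / 0.595) = Φ(−1.165) = 12%.

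**Step 2, sample counts.** On the Day 1 and Day 14 schedule, samples fall at about weeks 2, 4, 6 and so on, plus Visit 801. Progression at week 6 gives 3 + 1 = 4 samples; week 12, 6 + 1 = 7; week 18, 9 + 1 = 10; week 24, 12 + 1 = 13.

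**Step 3, maximum of k values.** For a flat marker, the chance that at least one of k samples shows a reduction of r or more is 1 − ∫ φ(z)[1 − Φ(ln(1 − r)/0.42 + z)]^k dz.

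| Samples | Median maximum reduction | Chance of at least 50% |
|---|---|---|
| 4 | 35% | 30% |
| 7 | 43% | 40% |
| 10 | 47% | 46% |
| 13 | 50% | 50% |

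**Step 4, listings of 47 patients.** Median TTP 18 weeks, marker unrelated to TTP. Mean rank correlation of maximum reduction with TTP (0 if unbiased):

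| Scenario | Twice per cycle |
|---|---|
| No drift, no early stopping | 0.28 |
| No drift, early stopping | 0.18 |
| No drift, early stopping, 4 weeks past progression | 0.13 |
| Marker rising 2%/week, early stopping | 0.07 |
| Marker rising 2%/week, early stopping, 4 weeks past progression | 0.04 |

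With one sample per cycle, the three no-drift scenarios give 0.12 to 0.27.

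**Step 5, alternatives.** Best change by week 8, in patients still progression-free then and with time counted from week 8, gives a mean rank correlation of 0.00 to 0.01 in every scenario. Response to date as a time-dependent covariate gives a hazard ratio of 0.99 to 1.01.

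**The case against.** The strongest reply is that this is a patient listing with an optional summary. No hazard ratio, correlation or test is planned, and SAP 5.3.3 rules out formal efficacy testing based on power calculations. The listing also shows the time to the maximum. The same section provides line plots over time and a mixed model by sampling time, and SAP 5.1.3 has an 8-week AFP response rule. All of this stands and makes the point low priority. It does not correct the pairing, however: a late maximum becomes visible but is not discounted, and the other analyses do not govern this listing. Table shells might set a window. The SAP does defer some detail (of its interim marker models, in 5.3.2: "Specific details of these analyses will be provided in the TFL shells and requirements"), but the shells were not available and the SAP text sets none.

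A reader might infer more than the documents support:
- **That AFP is badly affected.** Protocol 12.2.3 treats AFP elevation as a marker of progression, and treatment past progression is allowed from Amendment (b). Under the assumptions closest to that, the bias nearly vanishes.
- **That every marker has the twice-per-cycle counts.** MAP panel, Fibrotest and immunophenotype do not.
- **That the categorical rule has a calculable bias.** It also lacks a window, but the documents name no categorical marker that is sampled repeatedly on treatment, so no size can be given.
- **That the primary objective is compromised.** Protocol 12.1 includes the biomarker-efficacy relationship in that objective; protocol 6.1 and SAP 4.1 do not.

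**Conclusion.** The concern holds in limited form. As written, the listing invites a comparison that favours markers in patients with long TTP, for any marker without drift against its hypothesized direction. The illustrative size is a rank correlation of about 0.13 to 0.28 without drift, depending on early stopping and treatment past progression, and about 0.04 for AFP rising 2% per week with both. These figures rest on the assumptions above and on AFP's CV. The documents give no CV for other markers, so the size for E-cadherin or TGF-beta is unknown. The Kaplan-Meier TTP estimates and the mixed-model marker analyses are not affected, and no decision rule depends on the listing. It is a cheap improvement of low priority, most useful for Part C, whose data were still maturing at Amendment (e).

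**What to change.** Keep the maximum-change listing as description only. Add two columns, the number of post-baseline samples and the change by week 8, and a note that the listing is not evidence of association.

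For any statement that relates marker response to TTP, use one of these:
- response by a week-8 landmark in patients still progression-free and in follow-up, with time counted from the landmark; or
- response to date as a time-dependent covariate in a Cox model.

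For the sustained AFP criterion, first reconcile the definitions. SAP 5.1.3 says that "a sustained reduction of 50% over 3 months is a relevant change suggesting a treatment effect", while protocol 12.2.9 takes at least 2 months as reasonably sustained. Then use the time-dependent form, with the status switching only when the criterion is met.

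Apply this to Part C, check the matching text in later SAP versions (not available here), and label any re-analysis of Parts A and B post hoc.

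The cost is SAP wording and modest programming, with no new data. With 6-weekly scans, the week-8 landmark loses patients whose progression is found at week 6: 1 − 0.5^(6/12) = 29% at a 12-week median TTP and 1 − 0.5^(6/18) = 21% at 18 weeks. The time-dependent model drops none.
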